8.3 Viral Serology

At screening, the following viral serology assessments will be performed: Hepatitis B Surface Antibody (HBsAb), Hepatitis B Surface Antigen (HBsAg), Hepatitis C Virus Antibody, Human Immunodeficiency Virus (HIV). The results of HBsAb, HBsAg, and Hepatitis C Virus Antibody will be classified as “Negative”, “Gray zone”, “Positive” or “Not done” with specification. Also, the results of HIV will be classified as “Negative”, “Positive” or “Not done” with specification. A listing and table will be produced for the safety population.

8.4 Medical History

Medical history is defined as a medical event or condition that will be recorded as part of the subject’s medical history if the onset of the event occurs before the ICF is signed.

Medical history will be summarized by treatment group with number and percentage and displayed by System Organ Class (SOC) and Preferred Term (PT). SOCs will be presented in alphabetical order and within each SOC, the PTs will also be presented in alphabetical order in the ITT, ITTI and PK populations. Subjects that have more than one prevalence per PT within each SOC will be counted only once. Medical history will also be listed for the ITT population.

Medical histories will be coded using the Medical Dictionary for Regulatory Activities (MedDRA) version 20.1 or later, and the version number will be shown as a footnote on the corresponding tables and a listing.

9. Treatments and Medications

9.1 Prior and Concomitant Medications

Use of all medications (drugs taken from 30 days prior to randomization until Day 110 or EOS visit) will be

Statistical Analysis Plan

recorded in the subject's eCRF.

A prior medication is defined as any medication with end date prior to the exposure to study drug.

A concomitant medication is defined as any medication that is ongoing, or has an end date that is on or after the date of study drug infusion. The start date of a concomitant medication can be before or after the date of first infusion. If the last taken time of medication and study drug infusion are available, then the time will be considered with date in determining the prior/concomitant medication.

If a subject takes specific medication several times within specific period of observation (i.e. prior or concomitant), then that medication is only counted once within the period where it is taken.

Prior and concomitant medications will be summarized by treatment group for safety population with number and percentage and displayed by Drug Class (Level 2) and PT. Drug Class will be presented in alphabetical order and within each Drug Class, the PTs will also be presented in alphabetical order. At each level of subject summarization, a subject is counted only once if a subject reported one or more medication at that level. When Anatomical Therapeutic Chemical (ATC) Level 2 for Drug Class is not available, Level 1 will be used instead.

Prior and concomitant medications will be identified in a listing for the ITT and safety population.

For the purpose of inclusion in prior or concomitant medication tables, incomplete medication start and end dates will be imputed as described in [Appendix 14.3.1](#). A listing will display actually recorded (no imputed) dates in eCRF.

Prior and concomitant medications will be coded using the ATC classification of World Health Organization Drug Dictionary (WHODD) version September 2017 or later, and the version number will be shown as a footnote on the corresponding tables and listings.

9.2 Study Drug Exposure

Study drug exposure will be summarized by treatment group with number and percentage of the subjects who received full dose, partial dose, or are not administered study drug. The planned and administered dose (mg) of study drug will be also summarized using descriptive statistics.

A listing will be provided by treatment group showing the details of study drug exposure including actual administered dose for each subject. The actual administered dose will be calculated as Dose (45mg/kg or 90mg/kg for CT-P27 groups and 90mg/kg for Placebo group)*Weight at screening if a subject was administered planned dose. In case, the recorded weight is not correct, the actual administered dose will be calculated using weight recorded on the deviation list. This analysis will be performed on the safety population.

9.3 Use of Drugs for Symptom Relief

Drugs for symptom relief will be confirmed based on the recorded medications with "Yes" for the question, 'Is this drug used for symptom relief?' of the 'Prior and Concomitant Medications' page of eCRF.

Drugs for symptom relief will be summarized in a table in a similar manner to the table of concomitant medication described in section 9.1 for the ITT population.

Incomplete start date/time or end date/time of drugs for symptom relief will be imputed as described in [Appendix 14.3.2](#).

10. Efficacy Analysis

10.1 Primary Efficacy Analysis

The primary efficacy endpoint analysis will assess the time from the administration of study drug to resolution of influenza symptoms and fever. The Flu-iiQ™ and body temperature recorded in diary including records as

Statistical Analysis Plan

a part of suspicious ADE assessment will be used for the analysis. The Flu-iiQ™ is a validated questionnaire with four domains. This includes the Domain 1; intensity of influenza symptoms, Domain 2; impact on activities, Domain 3; effects on feelings and Domain 4; concerns due to influenza. Subjects are offered four choices, ranging from the most positive response (e.g., none or not at all) to the most negative choice (e.g., severe or great difficulty). This analysis will be performed on the ITTI population.

The definitions of resolution of influenza symptoms and fever are described below.

Resolution of symptoms has occurred if all of the following influenza symptoms (as recorded on the Flu-iiQ™ of Domain 1) are mild in intensity or none for at least 24 hours. (4-point scale - 0: None, 1: Mild, 2: Moderate, 3: Severe).

- Respiratory symptoms (cough, sore throat, and nasal congestion)
- Constitutional symptoms (headache, feeling feverish, body aches and pains, and fatigue)

Resolution of fever is defined as:

- Body temperature (as recorded in the diary) of $<37.0^{\circ}\text{C}$ for at least 24 hours.

The start time for resolution of influenza symptom and fever is defined as the start time when symptoms and fever are resolved, whichever occurred latest.

The time (in days) from the administration of study drug to resolution of influenza symptoms and fever will be calculated as follows: [Start date/time of resolution of influenza symptoms and fever] – [Start date/time of study drug administration]. If time of completion of diary for Flu-iiQ™ and body temperature is missing then the time will be assumed to be 10:00 AM and 10:00 PM for Morning and Evening, respectively.

If the subject has received the drugs for symptom relief, the effective duration of the drugs for symptom relief should be considered in determining the start time for resolution of symptom and fever.

For example, the study drug was administered at 12:00 on 1st day. The first time body temperature recorded $<37.0^{\circ}\text{C}$ in the diary was 10:00 on 2nd day and continued more than 24 hours. But acetaminophen/paracetamol known to be effective for 6 hours had been administered at 09:00 on 2nd day [1 hour prior to the time when the body temperature decreased $<37.0^{\circ}\text{C}$], it will be calculated that the start time point for body temperature $<37.0^{\circ}\text{C}$ is 15:00 on 2nd day [27 hours after the study drug administration]. Then, if the next time body temperature recorded $<37.0^{\circ}\text{C}$ in the diary since 15:00 was 22:00 on 2nd day and body temperature was $<37.0^{\circ}\text{C}$ for 24 hours from then, the start time for resolution of fever is 22:00 on 2nd day [34 hours after the study drug administration].

Drugs for symptom relief will be discussed during blinded DRM (14.5). Only drugs for symptom relief with an effective duration overlapping the primary endpoint duration (from a day of resolution start to resolution end) will be considered as drugs that affect the result of primary efficacy analysis. Effective durations of each drug will be discussed during blinded DRM too.

The primary efficacy endpoint will be analyzed using a Wilcoxon rank-sum test to assess differences between treatment groups (CT-P27 45 mg/kg vs placebo, CT-P27 90 mg/kg vs placebo), if every subject is followed until resolution of influenza symptoms and fever. The Wilcoxon rank-sum test will be used to test for a statistical significant difference of time to resolution between placebo and CT-P27. The results of the analysis will be summarized using p-values. The significant level will be set to 5%. If p-value is lower than 5%, it is considered that there is a significant difference between placebo and CT-P27. For subjects who withdrew from the study before the symptoms have resolved or if the symptoms did not resolve until the data cut-off, data will be censored at the latest date/time recorded on the diary or start date/time of study drug administration when there are no recorded data on the diary after study drug administration. If there is any censoring, the primary efficacy endpoint will be analyzed using Log-rank test and Gehans Wilcoxon test, and the result will be presented by p-values from the two tests. Also the table will present count of censoring reasons and 25th percentile, median, 75th percentile of time from administration of study drug to resolution. Kaplan-Meier plots will be presented.

CONFIDENTIAL

Statistical Analysis Plan

If there are no censoring data, sensitivity analysis using tipping point analysis under Missing Not at Random (MNAR) will be also performed to explain varying cases about average unobserved outcomes dropouts on two treatment groups.

Sensitivity Analyses which alter resolution conditions of primary efficacy analysis will be performed on the ITTI population. Following two endpoints will be assessed as described for the primary efficacy endpoint.

- Time (in days) to resolution of influenza symptom (respiratory and constitutional symptoms)

In the analysis, fever is not considered and the definition of resolution of symptom is the same as those of primary efficacy analysis.

- Time (in days) to resolution of influenza symptom and fever

In the analysis, threshold of resolution of fever is changed to 37.8°C and the definition of resolution of symptom is the same as those of primary efficacy analysis.

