Approximately 183 subjects with influenza A to be enrolled in the study will be randomly assigned to 1 of 3 groups, CT-P27 45 mg/kg, CT-P27 90 mg/kg, or placebo (approximately 70 subjects per CT-P27 treatment groups and 43 subjects in placebo group). Randomization will be stratified by flu vaccination history within a year (Yes vs No) and participation in Pharmacokinetic (PK) sub-study (Yes vs No). A schematic diagram of

CONFIDENTIAL

Statistical Analysis Plan

subject assignment is presented in Figure 2.

[figure not shown]
Figure 2 Schematic diagram of Subject Assignment

All enrolled subjects will be given a single dose of CT-P27 45 mg/kg, CT-P27 90 mg/kg, or placebo intravenously over 90 minutes (± 15 minutes) on Day 1 and then followed by Day 110.

A PK sub-study will be performed on the subjects who signed informed consent to participate in a PK sub-study. Of total number of subjects to be enrolled, approximately 53 subjects (20 subjects per CT-P27 treatment groups and 13 subjects in placebo group) will be included in the Subgroup (PK) Cohort, and additional PK samples from the subjects in this cohort will be collected according to the schedule of assessments. A schematic diagram for the study cohorts is presented in Figure 3.

Figure 3 Schematic Diagram for the Study Cohorts

Subjects may be admitted to a hospital from Day 1 (before study drug administration) to Day 3 (after completion of the 48 hours assessments) if deemed necessary by the investigator's judgement. The first analysis of data will occur after all subjects have completed the assessments scheduled for Day 15.

CONFIDENTIAL

Statistical Analysis Plan

As study recruitment was conducted through 2 influenza seasons to reach the expected sample size, approximately 1-year gap has been made between the subjects who enrolled during first season (randomized before 30Apr2017) and second season (randomized from 01May2017). To include as much available data as possible in the 1st Clinical Study Report (CSR), the whole data up to Day 110/EOS visit for the first season subjects, and the data up to Day 15 for the second season subjects will be summarized in the 1st CSR. In the Follow-Up CSR, the whole data up to study close will be included and summarized.

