5.2 Determination of Sample Size

This study is designed to obtain effect sizes of 2 different CT-P27 treatment groups and placebo group based on the time from the administration of study drug to resolution of influenza symptoms and fever.

For this proof-of-concept dose-ranging study, assuming 90% of subjects are included in the eligible infected population, the total eligible sample size of 164 (63 eligible infected subjects per CT-P27 treatment groups and 38 subjects in placebo group) achieves 80% power to detect 1.8 days of reduction for the primary endpoint of time to resolution with 5% two-sided significance level and SD of 3 days using a Wilcoxon's rank-sum test.

Considering a dropout rate of 10%, this study will need 183 subjects to be enrolled to achieve 164 evaluable subjects.

For an effect size of 1.5 days of reduction in time to resolution with SD of 2.9 days, the total sample size could be increased to about 250 to achieve at least 80% statistical power with 5% two-sided significance level.

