12.9 Suspicious ADE

Subjects will be considered to possibly have ADE if they meet any of the following criteria:

- Symptoms have not resolved or have worsened up to Day 8 after the administration of study drug in the opinion of the investigator
- The subject develops a secondary influenza-like illness after Day 8

Subjects with suspicious ADE will be required to assess virus titer using the nasopharyngeal swab sample, Flu-iiQ™ and body temperature up to Day 8 after the day of ADE occurrence. If symptoms have not resolved or have worsened up to Day 8 after the day of ADE occurrence, same procedures will repeat.

The number and percentage of subjects who meet the criteria for suspicious ADE will be presented by actual treatment group.

Data recorded in 'Suspicious ADE' page of eCRF will be listed in listings for Flu-iiQ™, body temperature and virus titer of nasopharyngeal swab samples which are collected in scheduled visits.

13. Changes to Protocol-Specified Analysis

- The analysis scope for the 1st CSR is extended up to Day 110/EOS for subjects who enrolled in the first season to obtain sufficient data. (currently specified in 8.0 section of the protocol, but updated in 1.1 section of SAP)
- The definition of ITT population is changed to exclude subjects who are screening failures but randomized by accident. (currently specified in 8.4.1 section of the protocol, but updated in 5.3 section of the SAP)
- The definition of safety population is changed to include all subjects who receive any amount of study drug even if it's only the normal saline solution but to analyze such subjects as the placebo group. (currently specified in 8.4.3 section of the protocol, but updated in 5.3 section of the SAP)
- The sensitivity analysis using tipping point analysis will be performed only when there is no censoring case. (currently specified in 8.6.1 section of the protocol, but updated in 10.1 section of the SAP)
- Handling of BLQ values after administration of study drug is updated. (currently specified in 8.5.3 section of the protocol, but updated in 11.1.1 section of the SAP)
- Description of %AUCex is updated according to the European Medicines Agency's guidance in "GUIDELINE ON THE INVESTIGATION OF BIOEQUIVALENCE". (CPMP/QWP/EWP/1401/98 Rev. 1)

CONFIDENTIAL

Statistical Analysis Plan

(CHMP 2010). (currently specified in 8.5.3 section of the protocol, but updated in 11.1.2 section of the SAP)

- Sensitivity analyses of primary efficacy analysis are added.

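### The primary analysis takes in every suspicious-ADE diary, so recovery from a different illness weeks later can be scored as resolution of the index influenza

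*SAP*

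**What the plan says.** - **Scheduled diary.** Protocol 6.1.1 and Table 1 have every subject record Flu-iiQ and temperature twice daily from Day 1 to Day 8, and no longer.
- **Event.** SAP 10.1 requires all seven listed symptoms to be none or mild, and diary temperature to be below 37.0°C, each for at least 24 hours. The event time is the later of the two starts.
- **Extra data.** The same section says that diary records, including those made as "a part of suspicious ADE assessment will be used for the analysis".
- **What opens an ADE diary.** SAP 12.9 and Protocol 6.2.5 give two criteria. The first is symptoms that the investigator considers unresolved or worse by Day 8. The second is: "The subject develops a secondary influenza-like illness after Day 8". Either starts about a week of diary, repeated while symptoms persist.
- **Everyone else unresolved.** SAP 10.1: "data will be censored at the latest date/time recorded on the diary".
- **Tests.** With any censoring, log-rank and Gehan's Wilcoxon are both reported, with quartiles and Kaplan-Meier plots.

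Protocol 8.5.1 does not mention ADE diaries in the primary analysis, and SAP section 13 does not list their use as a change.

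**The concern.** There are two separate problems.

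1. **Wrong illness.** SAP 10.1 admits diaries from both ADE criteria. It has no rule tying the event to the index illness, sets no latest date, and does not say that the first resolution is the one that counts. Diaries from a new illness can supply the event time.
2. **Outcome-dependent follow-up.** Whether an unresolved subject is observed past Day 8 rests on the investigator's view of symptoms. The endpoint rests on seven diary items plus temperature, each held for 24 hours. Where the two disagree, the subject is censored at about Day 8 while subjects judged still ill stay at risk. Kaplan-Meier and log-rank methods assume that censoring carries no information about the remaining time.

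SAP 1.1 says the study is to establish an effect size and inform dose selection, so distortion of the late curve matters even if the test keeps its level.

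**Working it through.** **1. The plan's own figure.** SAP 5.2 has "63 eligible infected subjects per CT-P27 treatment groups and 38 subjects in placebo group", and says that this "achieves 80% power to detect 1.8 days of reduction for the primary endpoint", "with 5% two-sided significance level and SD of 3 days using a Wilcoxon's rank-sum test".
- Standard error factor: √(1/63 + 1/38) = 0.2054. Standardised effect: 1.8/3 = 0.6.
- Normal form: 0.6/0.2054 − 1.96 = 0.961, so power is 83.2%. With the Wilcoxon efficiency 3/π: 0.6 × 0.977/0.2054 − 1.96 = 0.894, so 81.4%.
- Enrolment: 164/0.9 = 182.2, so 183.

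The stated figures reproduce. They include no placebo mean, no end of follow-up and no flagging rate, so everything in steps 3 to 5 rests on assumptions.

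**2. The new-illness route, traced through the text.** Suppose symptoms resolve on Day 4 but diary temperature stays at 37.1°C to Day 8.
- There is no event by Day 8. Criterion 1 concerns symptoms, so the investigator may not flag the subject.
- An influenza-like illness begins on Day 40. Criterion 2 opens a diary, and from Day 45 all items qualify for 24 hours.
- Under SAP 10.1 as written, the event is at 45 − 1 = 44 days after dosing. The subject counts as at risk from Day 8 to Day 40 with no diary.
- For the secondary temperature endpoint, SAP 10.2 excludes measurements more than 24 hours apart as not consecutive. SAP 10.1 has no such rule, and that rule would not block a fresh 24-hour run anyway.

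**3. How many could be unresolved.** Assume infusion between 08:00 and 18:00 and a last Day 8 entry between 18:00 and 22:00. The diary then ends 7.0 to 7.6 days after dosing. Since 24 hours must be confirmed, the last usable start is day 6.0 to 6.6; I use 7.4 and 6.4. Assume gamma times with SD 3 (shape (mean/3)², scale 9/mean) and CT-P27 1.8 days faster.

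| Placebo mean (assumed) | Start after day 7: placebo / CT-P27 | Start after day 6.4: placebo / CT-P27 |
|---|---|---|
| 4 days | 14.4% / 7.1% | 17.8% / 8.5% |
| 5 days | 21.5% / 10.5% | 26.6% / 12.9% |
| 6 days | 31.5% / 15.6% | 38.3% / 19.3% |

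These are all unresolved subjects, flagged or not.

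**4. Effect on the late curve.** Assume that those with more than 2 days of illness left at day 7.4 are always flagged, those with less are flagged with probability p, and those who start resolving in the last 24 hours are not flagged. With S(t) the true proportion unresolved, Kaplan-Meier resolution at day 10 is

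1 − S(6.4) × S(10) / {p[S(7.4) − S(9.4)] + S(9.4)}.

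For mean 5 and p = 0.3: 1 − 0.266 × 0.068/(0.3 × 0.100 + 0.086) = 0.84, against a true 0.93. For mean 6 the result is 0.78 against 0.90. Over p = 0.1 to 1.0 the shortfall is 3 to 12 points (mean 5) and 4 to 17 points (mean 6). For mean 6 and p = 0.3, the curve stands at 0.65 at day 8 and 0.78 at day 10, so the 75th percentile falls between those days; the true value is 7.7.

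**5. Effect on the test.** I simulated the log-rank test, 63 against 38, with 1,500 runs per setting and placebo means 5 to 7.
- Equal flagging in both arms: type I error 4.4 to 5.7%.
- Flag probability 0.6 in one arm and 0.2 in the other: 4.8 to 7.3%.
- A later illness counted as the event in 5% of Day-8-censored subjects: power moves about 1 point at means 5 and 6, and 3 to 4 points at mean 7.
- Power is 71 to 78% with flagging and 80 to 81% with common Day 8 censoring. This is not evidence of selection harm: complete follow-up gave only 68 to 70% in the same model.

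**6. Planned checks.** The two added sensitivity analyses alter only the fever condition. Tipping-point analysis is dropped once anyone is censored. None varies which diaries count.

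**The case against.** The other side has a good case on size.

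- Following slow resolvers past Day 8 is ordinary at-risk follow-up, and any late curve rests on them. Bias arises only where the investigator and the diary rule disagree. This stands: the percentages in step 3 are not the share informatively censored, though a reader might take them so.
- A reader might infer that the primary test is invalid. The documents do not support that. Investigators are blinded (Protocol 5.8), so equal flagging is the natural null case and type I error is then near 5%. The values above 6% need an invented difference between arms.
- The log-rank result does not stand alone, because Gehan's Wilcoxon gives late events less weight. A subject unresolved only at 37.1°C is dealt with by the no-fever and 37.8°C analyses. Both points stand, but those analyses use the same diaries, so they do not remove new-illness events.
- The new-illness route needs no diary resolution by Day 8, no flag, and a later illness. It is probably rare, and if first resolution is intended it cannot touch subjects already resolved. The SAP does not state that intention.
- A reader might also see a defect in the first report's mixed cut-offs: "the data up to Day 15 for the second season subjects will be summarized in the 1st CSR", against Day 110 for the first season. That difference is declared in SAP section 13, and a diary opened at Day 8 runs 168 hours, to about Day 15, so a full first cycle is covered.

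**Conclusion.** The concern holds as a gap in the event and follow-up rules. As written, SAP 10.1 lets recovery from a different illness count as the primary event, and it makes observation after Day 8 depend on a judgement that is not the endpoint.

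The size is not determinable: the documents give no placebo mean, flagging rate or later-illness rate. Under the stated assumptions, the late placebo curve could be a few to well over ten points too low. The placebo 75th percentile is exposed only where more than 25% are unconfirmed by Day 8, which is means 5 and 6 in the table but not mean 4 and not the CT-P27 arms. The harm is to estimation rather than to the level of the test.

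A reader might go on to conclude that Day 8 censoring must be the primary rule. That does not follow. It would discard legitimate late resolutions of the index illness, and it would make the 75th percentile inestimable in the very cases where that percentile is most in doubt. It belongs as a sensitivity analysis.

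**What to change.** In SAP 10.1:

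1. State that the event is the first resolution of the index illness.
2. State that diaries opened by a secondary influenza-like illness after Day 8 are not used for the primary endpoint, and that such subjects, if unresolved, are censored at their last index-illness diary entry.
3. Pre-specify a sensitivity analysis that censors every unresolved subject at the last scheduled Day 8 diary entry, reported beside the primary result.

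Record the use of ADE diaries in SAP section 13, since Protocol 8.5.1 does not provide for it.

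The cost is SAP wording and one more analysis. A few late events become censored. Safety follow-up for suspicious ADE is unchanged.

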6.1.1.1 Flu-iiQ™

The Flu-iiQ™ is a validated questionnaire with four domains. These include the 1) intensity of influenza symptoms, 2) impact on activities, 3) effects on feelings and 4) concerns due to influenza. Subjects are offered four choices, ranging from the most positive response (e.g., none or not at all) to the most negative choice (e.g., severe or great difficulty). Scores for influenza symptoms are none, mild, moderate, and severe.

The Flu-iiQ™ will be completed by subject at screening. After study drug administration, subjects will be instructed to complete the Flu-iiQ™ twice a day (at approximately 12-hour intervals) from Day 1 to Day 8 (in the morning [between 6 and 10 AM, approximately] and in the evening [between 6 and 10 PM, approximately]).

The results of the first two domains of the Flu-iiQ™ (those assessing symptoms and the impact of influenza on activities) will be used in the assessment of primary and secondary efficacy endpoints (see [Section 8.2](#)). The results of the 3rd and 4th domain (impact on feelings and concerns) will be evaluated as QoL measures. A copy of the Flu-iiQ™ is included in [Appendix 2](#). Information obtained from the diary will be transferred to the eCRF.

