8.2 Study Endpoints

8.2.1 Primary Efficacy Endpoints

The primary efficacy endpoint is defined as the time from the administration of study drug to resolution of influenza symptoms and fever.

Resolution of symptoms has occurred if the following influenza symptoms (as recorded on the Flu-iiQ™) are mild in intensity or none for at least 24 hours.

- Respiratory symptoms (cough, sore throat, and nasal congestion).
- Constitutional symptoms (headache, feeling feverish, body aches and pains, and fatigue).

Resolution of fever is defined as:

- Body temperature of <37.0°C for at least 24 hours.

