3.1 Efficacy Endpoints

Primary Efficacy Endpoint:

The primary efficacy endpoint is defined as the time from the administration of study drug to resolution of influenza symptoms and fever as recorded in the diary.

Resolution of symptoms has occurred if the following influenza symptoms recorded on the Influenza Intensity and Impact Questionnaire (Flu-iiQ™) in the diary are mild in intensity or none for at least 24 hours.

- Respiratory symptoms (cough, sore throat, and nasal congestion)
- Constitutional symptoms (headache, feeling feverish, body aches and pains, and fatigue)

Resolution of fever is defined as:

- Body temperature of <37.0°C for at least 24 hours

Secondary Efficacy Endpoints:

- Time to resumption of normal activity as reported in Domain 2 of the Flu-iiQ™
- Time to return to normal body temperature (<37.0°C) for at least 24 hours
- Time to resolution of individual symptoms for at least 24 hours as reported in Domain 1 of the Flu-iiQ™
- Severity of symptoms as reported in Domain 1 of the Flu-iiQ™
- Viral shedding in nasopharyngeal swab samples
- Incidence of secondary complications of influenza
- Quality of Life (QoL) measures as reported in Domain 3 and Domain 4 of the Flu-iiQ™
- Physician assessment

Statistical Analysis Plan

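### SAP 10.1 dates the primary event from the later of two separate 24-hour windows and does not state that symptoms and temperature must be resolved together

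*SAP*

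**What the plan says.** Protocol 8.2.1 sets the endpoint: "The primary efficacy endpoint is defined as the time from the administration of study drug to resolution of influenza symptoms and fever". It then lists a symptom criterion and a fever criterion, each with its own 24-hour duration. SAP 3.1 and 10.1 keep that structure.

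- Symptoms (SAP 10.1): "Resolution of symptoms has occurred if all of the following influenza symptoms" (three respiratory, four constitutional) are none or mild for 24 hours.
- Fever (SAP 3.1): "Body temperature of <37.0°C for at least 24 hours".
- Composite (SAP 10.1): dated from "the start time when symptoms and fever are resolved, whichever occurred latest".

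The event time is that composite start minus the start of dosing. The worked example in SAP 10.1 derives the fever start from temperature and symptom-relief drug use alone; symptoms play no part in it. The diary (Protocol 6.1.1.1) is completed "twice a day (at approximately 12-hour intervals) from Day 1 to Day 8".

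**The concern.** A composite of symptoms and fever should describe a state in which the subject is free of both. Taking the later of two start times gives that state only if the component that resolved first is still resolved when the second one starts, and stays so for 24 hours. Nothing in SAP 10.1, in the missing-data rules of SAP 10.3.1 or in Protocol 8.2.1 and 8.5.1 says so, and nothing deals with temperature or symptoms that return after a first qualifying window.

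Two outcomes are possible for such a subject: an event time that is earlier than the first 24 hours free of both, or an event where no such 24 hours exist in the diary. At the least, two programmers could derive different primary endpoints from the same data. The definition also affects who is censored, and under SAP 10.1 any censoring moves the primary test from the Wilcoxon rank-sum test to the log-rank and Gehan tests.

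**Working it through.** **1. The plan's own figures.** In the SAP 10.1 example, dosing is at 12:00 on day 1 and "the start time for resolution of fever is 22:00 on 2nd day [34 hours after the study drug administration". From 12:00 on day 1 to 22:00 on day 2 is 24 + 10 = 34 h, as stated. The design power also reproduces. With 63 and 38 evaluable subjects, a 1.8-day reduction, SD 3 days and rank-sum efficiency 3/π (SAP 5.2), power = Φ(1.8 / [3·√((π/3)(1/38 + 1/63))] − 1.96) = Φ(2.85 − 1.96) = 81.4%. Simulating the test on normal data gives 79.9%; the plan states 80%. Enrolment is 164/0.9 = 182.2, rounded up to 183. None of these depends on the point at issue.

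**2. Two rules on one constructed diary.** Dose at hour 0, entries every 12 hours, no symptom-relief drug, no missing entries.

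| Hour | 10 | 22 | 34 | 46 | 58 | 70 | 82 | 94 | 106 | 118 | 130 | 142 | 154 | 166 | 178 |
|---|---|---|---|---|---|---|---|---|---|---|---|---|---|---|---|
| Temp °C | 38.4 | 37.6 | 36.8 | 36.7 | 36.8 | 36.9 | 38.2 | 38.3 | 38.1 | 38.0 | 37.4 | 36.8 | 36.7 | 36.6 | 36.6 |
| Worst symptom | 3 | 3 | 2 | 2 | 2 | 2 | 1 | 1 | 1 | 1 | 1 | 1 | 1 | 1 | 1 |

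- Written rule: first 24-hour fever window starts at 34 h and first 24-hour symptom window at 82 h. Event = max(34, 82) = 82 h = 3.42 days. The temperature at 82 h is 38.2°C.
- Joint rule (both criteria met at every entry of one 24-hour window): event = 142 h = 5.92 days, which is 60 h = 2.5 days later.
- Variant with temperatures of 37.4, 37.2, 37.3, 37.1 and 37.2°C from hour 130 on: the written rule still gives 82 h. The joint rule gives no event and censors at 178 h, if no further diary is kept.
- At the 37.8°C threshold of the planned sensitivity analysis, the first diary has a fever start of 22 h, so the written rule gives max(22, 82) = 82 h and the joint rule 130 h. That analysis inherits the gap.

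**3. How often the rules differ, under assumptions.** The documents give no rate of return of temperature or symptoms, so every input here is assumed.

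- *Exceedance model.* 16 half-day readings; defervescence and symptom resolution gamma-distributed (shape 4) with means of 2 and 4.5 days. Morning/evening chances of a reading at or above 37.0°C after defervescence are 2/5%, 5/10%, 5/20% and 10/30%. The joint rule gives a later or censored time in 7%, 14%, 22% and 30% of subjects counted as resolved.
- *Temperature-noise model.* Temperature falls exponentially from 38.5 towards 36.6°C (median time constant 48 h) and symptoms fall likewise (72 h), with autocorrelated noise. For temperature noise SD of 0.1, 0.2, 0.3 and 0.4°C, the rules differ in 3.0%, 4.8%, 8.6% and 11.2% of resolved subjects. At the assigned event time 0.03% to 2.3% have a reading at or above 37.0°C, and none at or above 38.0°C.

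**4. Effect on the comparison.** In the exceedance model with an assumed true 1.8-day difference in symptom time, the between-arm differences are:

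| Exceedance (AM/PM) | Written rule (days) | Joint rule (days) | Gap |
|---|---|---|---|
| 2/5% | 1.84 | 1.85 | 0.01 |
| 5/10% | 1.84 | 1.86 | 0.02 |
| 5/20% | 1.79 | 1.83 | 0.04 |
| 10/30% | 1.75 | 1.84 | 0.09 |

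**The case against.** **The wording can be read as a joint state.** The composite sentence speaks of the time when symptoms and fever are resolved, and the symptom-relief paragraph of SAP 10.1 refers to a single endpoint period with one start and one end. Both fit a sponsor who had one shared window in mind. This stands as a possible intention. It does not settle the text, because choosing whichever is later selects between two times and no section states concurrency.

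**A reader might infer that subjects will be scored as resolved while clinically febrile.** The documents do not support that as an expected event. Fever at entry means 38.0°C or more, whereas 37.0°C is a strict endpoint cut-off, and the 38.2°C case above was built by hand. The symptom criterion also requires feeling feverish to be mild or none, which makes the case rarer without excluding it.

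**The simulations show disagreement between rules, not error in the written one.** The exceedance model contains stray readings in subjects who have truly defervesced, and no real relapse. Measured against true resolution in that model, the written rule is never early. It is late in 3% to 21% of subjects, by 0.03 to 0.29 day on average over all subjects. The joint rule is late in 10% to 50% (counting those newly censored), by 0.09 to 0.56 day. This stands as a real cost of a joint rule at so low a cut-off.

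**The sensitivity analyses already probe the 37.0°C component.** One drops fever and the other uses 37.8°C. That helps with isolated low readings, but neither imposes a shared window.

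**Conclusion.** The concern holds as a defect of definition in the primary endpoint. The written rule can return an event time, or an event, for a subject who never had 24 hours free of both components, and the gap is open in both directions (temperature or symptoms returning). It should be corrected because a short change using data already collected closes it.

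The size is not known. The range of roughly 3% to 30% of resolved subjects with a later or censored time rests wholly on assumed exceedance rates and temperature noise. A reader might go further and set the average delay in individual times against the 1.8-day target. That comparison is not valid: the delay is a within-subject shift under a rule common to all blinded arms, while 1.8 days is a difference between arms. Where the between-arm difference was computed it moved by 0.01 to 0.09 day, under one assumed model. Bias in the treatment comparison is therefore not shown, and the stated power and sample size are untouched.

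**What to change.** In SAP 10.1, replace the composite sentence with a joint definition. The event is the start of the first period of at least 24 hours in which all seven symptoms are none or mild and temperature is below 37.0°C at every available diary reading in that period. Add that if either component lapses before the 24 hours are complete, the period starts again.

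- Keep the SAP 10.3.1 allowance for a single missing middle temperature reading and the SAP 10.1 handling of symptom-relief drugs, both applied to the joint window. This also gives the symptom-relief paragraph one defined endpoint period.
- Apply the same joint rule to the 37.8°C sensitivity analysis with its own threshold.
- Report the current later-of-two-starts version as a further sensitivity analysis, so that the effect of the change is visible.
- Record the clarification in SAP section 13.

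The cost is one or two sentences and a small derivation change, with no new data. Some subjects will get later or newly censored times. New censoring can trigger the log-rank and Gehan branch and, under SAP 10.1 and 13, removes the tipping-point analysis, which is planned only when nothing is censored. The joint rule is also more sensitive to isolated readings just above 37.0°C, so the 37.8°C analysis should be read alongside it.
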